5.6.4. Laboratory Evaluations

Data for the following coagulation, hematology, and biochemistry analytes received from local laboratory are to be measured at the scheduled visits indicated in the study flowchart.

All parameters recorded in the study will be included in the listings, but only parameters defined in

[Table 7](#) specifies the tests that will be included in the summaries.

Table 7 Laboratory Tests to Be Included in Summaries

Hematology Test (SI unit)	Biochemistry Test (SI unit)	Coagulation

○ Hemoglobin (g/L)○ Differential WBC ($10^9/L$ and %)
• Neutrophils• Lymphocytes○ Absolute lymphocyte count○ Platelet count ($10^9/L$)	
○ Alanine aminotransferase (ALT) (U/L)○ Aspartate aminotransferase (AST) (U/L)○ Total Bilirubin (mmol/L)○ Lactate Dehydrogenase○ Alkaline phosphatase (U/L)○ C-reactive protein○ Albumin (g/L)○ Creatinine (mmol/L)○ Creatinine Clearance (mL/s)	
○ D-dimer

All laboratory data will be reported in SI units. All quantitative laboratory test values at each assessed visit will be compared with the relevant reference range in SI units and categorized as:

Low: Below the lower limit of the reference range.

Normal: Within the reference range (upper and lower limits included).

High: Above the upper limit of the reference range.

For analysis purposes, values preceded by a “ $<$ ” or a “ $>$ ” sign (i.e. those below or above the limits of quantification) will be considered equal to the lower or upper limit of quantification, respectively.

Laboratory data will be summarized by default descriptive summary statistics for continuous and categorical variables for the ASaT population by overall as follows:

- Observed values and change from baseline at each scheduled assessed visit for each standard continuous laboratory parameter

Listings of all clinical laboratory data including derived change from baseline will be provided for the screened population. Within each listing, laboratory values outside the normal ranges will be flagged as either high or low for applicable laboratory assessments.

Hematology, Coagulation and Biochemistry results for selected laboratory parameters for each scheduled visit will be displayed graphically using boxplots showing the summary data per scheduled assessment, including an overlaid mean profile line and approximate lower limit of normal reference range (LLN) and upper limit of normal reference range (ULN) reference lines indicated by overall for ASaT population.

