4.1.2 DLT definition

For the safety cohorts, DLTs will be AEs listed below, specified and graded according to CTCAE, version 5.0, without consideration of causality to nanrilefusp alfa. AEs listed below will be considered DLTs unless clearly not related to nanrilefusp alfa (i.e., events clearly due to cancer, other comorbid illness, or unequivocally related to concomitant medications).

Every DLT in the study will be discussed with the study investigators and every effort will be made to ensure all clinical assessments are carried out and documented appropriately and, wherever possible, histological assessments are also performed to identify and understand the safety profile of nanrilefusp alfa in combination with cetuximab.

AEs that are considered DLTs

- All grade 5 events not clearly related to disease progression or any other causes will be considered DLTs.
- Any grade 3 or higher non-hematologic toxicity regardless of duration will be considered a DLT, with the following exceptions that are not considered DLTs:
 - Grade 3 nausea, vomiting, or diarrhea that can be controlled within 72 hours
 - Grade 3 fatigue that lasts less than 5 days
 - Grade 3 or higher correctable electrolyte abnormalities that last less than 72 hours and are not associated with clinical complications
 - Grade 3 or higher serum amylase or lipase not associated with clinical manifestations of pancreatitis
 - Grade 3 aspartate aminotransferase (AST) or alanine aminotransferase (ALT) increase or grade 3 blood bilirubin increase that lasts 5 days or less
- Hy's law cases will be considered DLTs (see section [10.3](#)).
- Hematologic DLTs will include the following:
 - Grade 4 decreased neutrophil count or decreased platelet count lasting more than 7 days
 - Febrile neutropenia
 - Grade 3 or higher decreased platelet count with bleeding

AEs that are not considered DLTs

- Inflammatory reaction attributed to a local antitumor response (grade 3 tumor pain caused by acute inflammatory reaction at tumor-bearing sites, e.g., like sites of metastatic disease or lymph nodes) that resolves to grade 1 within 3 weeks
- Concurrent vitiligo or alopecia of any CTCAE grade

Other clinically significant toxicities, including a single event or multiple occurrences of the same event, may be considered DLTs in the safety cohorts.

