8.2.5.3 Biochemistry

Blood biochemistry tests will include Na, K, Cl, phosphate, Mg, Ca, albumin, total protein, ALT, AST, bilirubin (direct, total), alkaline phosphatase, lactate dehydrogenase, creatinine clearance calculated by the Cockcroft-Gault formula, creatinine, glucose (preferably fasting), urea or blood urea nitrogen, cholesterol, triglyceride, C-reactive protein, uric acid, amylase, and lipase.

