8.3.8 Reporting by the investigational site

8.3.8.1 AEs

Any AE, whether or not considered to be causally related to the trial medication and regardless of its seriousness, must be reported (described and recorded) in the AE section of the patient’s eCRF on an ongoing basis. Each AE will be evaluated by the investigator to determine its term and grade according to the CTCAE, version 5.0. In case a suitable CTCAE term is not available, an appropriate medical verbatim term may be used instead.

Only clinically relevant abnormal laboratory values, vital signs, or examination abnormalities need to be documented as AEs. Whenever possible, a diagnosis rather than symptoms should be provided on the AE eCRF page (e.g., anemia instead of low hemoglobin).

Clinically relevant here means: induce clinical signs or symptoms, require therapy (e.g., hematologic abnormality requiring treatment), require a change in trial medication(s), or require a change in the clinical trial schedule or per investigator’s discretion.

Physical examination findings will be compared with the baseline status and any significant change, as assessed by the investigator, must be documented as an AE.

A surgical procedure is not an AE but a therapeutic measure for a condition that necessitates surgery. Therefore, the condition for which the surgery is required has to be reported as an AE.

Any pre-planned surgery (i.e., planned before signature of the ICF) or other intervention permitted by this study Protocol and the condition leading to that measure are not AEs. In such cases, the underlying condition needs to be documented in the patient’s medical history on the eCRF.

Death itself is not an AE term but the outcome of an event, which needs to be described using medical terminology. Information about death will be captured on the respective eCRF page along with relevant details (date of death, immediate and underlying causes of death).

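### SAP 5.6.4 plans no table of patients by laboratory-derived CTCAE grade, so grade 3-4 values not reported as AEs go uncounted by grade, and electrolytes, amylase and lipase have no laboratory summary

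*SAP*

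**What the plan says.** Protocol section 3 makes safety laboratory findings part of a secondary safety endpoint. Protocol 9.3.3.2 says they will be summarised and leaves the detail to the SAP.

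SAP 5.6.4 separates listings from summaries: "All parameters recorded in the study will be included in the listings, but only parameters defined in" Table 7 go into summary tables. The one table item is "Observed values and change from baseline at each scheduled assessed visit for each standard continuous laboratory parameter", for the ASaT population overall. Values are also classified: "All quantitative laboratory test values at each assessed visit will be compared with the relevant reference range in SI units and categorized as" low, normal or high. Out-of-range values are flagged high or low in the listings.

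Protocol 8.2.5.3 collects more than Table 7 holds. Its list begins "Blood biochemistry tests will include Na, K, Cl, phosphate, Mg, Ca, albumin, total protein, ALT, AST, bilirubin (direct, total), alkaline phosphatase" and ends with "C-reactive protein, uric acid, amylase, and lipase".

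Two protocol rules decide what reaches the other safety tables. Under Protocol 8.3.8.1, "Only clinically relevant abnormal laboratory values, vital signs, or examination abnormalities need to be documented as AEs". Under Protocol 4.1.2, one exception to DLT status is "Grade 3 or higher serum amylase or lipase not associated with clinical manifestations of pancreatitis". Others cover brief, correctable electrolyte abnormalities without complications, and short-lived grade 3 AST, ALT or bilirubin increases.

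**The concern.** The usual summary of laboratory safety in an oncology trial is the number of patients whose worst value on treatment reached each grade. The SAP text does not call for it. A count of severe abnormalities is then available only for those the investigator chose to report as AEs, and that threshold is partly discretionary in an open-label trial. A severe value that was not reported remains in a listing, marked high or low but not graded.

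What is at stake is how complete the final report is on a stated secondary safety endpoint. The gap is widest for analytes that have no laboratory summary, and amylase and lipase are the clearest case, because the DLT route does not catch an asymptomatic rise either.

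**Working it through.** No sample size, power or error rate underlies this point. The check sets the analytes collected against those summarised, then follows a severe value through each planned table.

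**Analytes collected and summarised**
- Biochemistry in Protocol 8.2.5.3 has 24 items, counting direct and total bilirubin separately. Table 7 holds 9: ALT, AST, total bilirubin, LDH, alkaline phosphatase, C-reactive protein, albumin, creatinine and creatinine clearance.
- Electrolytes (Na, K, Cl, phosphate, Mg, Ca): 0 of 6 in Table 7.
- Amylase and lipase: 0 of 2. With the electrolytes, 0 of 8.
- Coagulation in Protocol 8.2.5.1: 1 of 5 (D-dimer).

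**Laboratory-type DLT exemptions (Protocol 4.1.2)**
- There are three: electrolytes; amylase or lipase; AST, ALT or bilirubin.
- Two of the three concern analytes absent from Table 7. The third concerns analytes in Table 7, which are summarised there as continuous values only.

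**Where a grade 3-4 value can be counted**
1. *Laboratory tables (SAP 5.6.4).* No table uses a laboratory-derived grade. SAP 5.1 includes minimum and maximum in the default statistics, so an extreme value of a Table 7 analyte at a scheduled visit can appear as that visit's minimum or maximum. This shows that an extreme occurred, not how many patients had one. The low/normal/high classes have no named table, and a count of high values would still not be a count by grade.
2. *Unscheduled samples (SAP 4.1.4).* These are listed and kept out of summaries, except for deriving post-baseline minimum or maximum values. SAP 5.6.4 names no laboratory table that uses those extremes, so unscheduled values enter no laboratory table.
3. *Hy's law (SAP 5.6.5).* Patients meeting the criteria are counted at each scheduled visit, and an eDISH figure is planned. This is a genuine laboratory-based patient count, but it needs raised aminotransferases and raised bilirubin together. It covers liver tests only and does not use grades.
4. *TEAE tables (SAP 5.6.3).* Patients are counted by SOC and PT for TEAEs of grade 3 or higher and by maximum CTCAE v5.0 grade. A laboratory abnormality enters if it was reported as an AE.
5. *DLT table (SAP 5.6.2).* DLTs come from a field on the AE page, so this table adds nothing for an unreported value.

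**Tracing two cases**
- A related grade 3 liver value leads to withholding under Protocol Table 6.2. That is a change in trial medication, so it must be reported under Protocol 8.3.8.1 and is counted in the TEAE tables.
- A grade 3-4 lipase rise without symptoms, treatment or schedule change is not a DLT and need not be an AE. If it is not reported, it is absent from routes 1 to 5 and remains only in the listing.

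**The case against.** The strongest reply is that the AE route already works. In the sponsor's earlier study (Protocol 2.3), decreased lymphocyte count was a TEAE in 66.7% of monotherapy and 47.6% of combination patients, and was among the commonest TEAEs above grade 2. Anything treated, or leading to a change of medication or schedule, must be reported, and that covers an electrolyte abnormality that is actively corrected. The endpoint wording attaches CTCAE severity to TEAEs rather than to laboratory findings. The trial is descriptive, every value is listed, and the table shells that SAP 5.1 refers to are not among the documents.

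Most of this stands, and it rules out three stronger readings that a reader might infer:
- *No table counts severe laboratory toxicity.* The TEAE tables count what was reported, and the Hy's law table counts patients directly.
- *Events exempt from DLT status disappear.* The exemption removes DLT status only. A reported event still enters the TEAE tables.
- *The dose decision is compromised.* Under Protocol 4.1.1 the internal safety committee reviews each safety cohort after its 21-day DLT period and does not wait for the final SAP tables.

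The reply does not remove the remaining gap. The lymphocyte figures show that some laboratory abnormalities are reported, but not that all severe ones are. A grade table in the shells cannot be excluded, but the SAP text does not call for one.

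**Conclusion.** The point holds as a modest reporting gap. Followed as written, the SAP yields no table by laboratory-derived grade and no laboratory summary for eight collected analytes. Apart from the Hy's law count, a grade 3-4 abnormality not reported as an AE is counted by grade nowhere. For a Table 7 analyte it shows at most as a visit minimum or maximum. Untreated, asymptomatic amylase or lipase rises are the most exposed.

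The documents give no rate of unreported severe values, so the number of patients affected cannot be stated; it is zero if investigators report every grade 3-4 value. The denominator would be the ASaT population, not the 52 planned for the efficacy population. No data are lost, and neither the primary endpoint nor the committee's dose decision is touched. The change is still worth making, because the endpoint is a stated one and the data are already collected. The conclusion assumes that the unseen shells contain no such table.

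**What to change.** In SAP 5.6.4:
- Derive the CTCAE v5.0 grade for every gradable analyte. This is already the study's AE grading scale.
- Add a table of baseline grade against worst post-baseline grade in the ASaT population, overall and by starting dose. Starting dose is the clean label because patients begun at 9 µg/kg may move to 12 µg/kg in a later cycle (Protocol 4.1.1).
- Use all post-baseline samples, unscheduled ones included, with a matching exception in SAP 4.1.4.
- Add Na, K, Mg, Ca, phosphate, amylase and lipase to Table 7.

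If the shells already contain such a table, it is enough to name it in the SAP text. The cost is grade programming and one or two extra tables; no new data are needed.

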5.6.5. Hy's Law for Liver Function Tests

Hepatic function abnormality defined by an increase in AST and/or ALT to $\geq 3 \times \text{ULN}$ concurrent with an increase in total bilirubin to $\geq 2 \times \text{ULN}$ but without increase in alkaline phosphatase (i.e., alkaline phosphatase $< 2 \times \text{ULN}$) meets the criteria for Hy's law and raises the concern for drug-induced liver injury when no other cause is identified.

The summary of liver function tests will include the following categories, and the number and percentage of patients meeting Hy's Law at each scheduled visit during the on-treatment period will be summarized for ASaT population.

An eDISH figure displaying patients who reach $3 \times \text{ULN}$ for ALT or AST, plus $2 \times \text{ULN}$ for total bilirubin and thus are at risk for a drug induced liver injury according to Hy's law will be presented for ASaT population. A listing of patients at risk will also be presented for screened population.

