1.3 Schedule of activities

Cycle	Visit	Screening Up to 21 days before day 1 of cycle 1	Cycle 1					From cycle 2 onwards				End of treatment* Within 7 (+7) days after the last dose of nanrilkefusp alfa and/or cetuximab (whichever occurs later)	Follow -up	
			Day 1	Day 2 (±1 day)	Day 8 (±1 day)	Day 9 (±1 day)	Day 15 (±1 day)	Day 1 (±1 day)	Day 2 (±1 day)	Day 8 (±1 day)	Day 9 (±1 day)	Day 15 (±1 day)		
Informed consent¹	X													
Demography²	X													
Cancer³ and medical history	X													
K-RAS/N-RAS	X		Optional at disease progression											
Body height	X													
Pregnancy test	X (blood) ⁴	X (urine) ⁵						X (urine) ⁵					X (urine)	X (urine) **
Physical examination	X ⁴							X ⁷					X	X ⁸
Body weight and body surface area	X	X ⁹						X ⁹					X	
Vital signs	X	X ¹⁰	X ¹⁰	X ¹⁰	X ¹⁰	X ¹¹		X ¹⁰	X ¹⁰	X ¹⁰	X ¹¹		X	X ⁸
Hematology¹²	X	X ⁶	X ⁵	X ⁶	X ⁵	X ⁵		X ⁶		X ⁶		X ⁵	X	
Biochemistry¹²	X	X ⁶	X ⁵	X ⁶	X ⁵	X ⁵		X ⁶		X ⁶		X ⁵	X	
Coagulation¹²	X	X ^{6,13}		X ⁶		X ⁵		X ⁶				X ⁵	X	
Urinalysis	X ⁴							X ¹¹					X	
Creatinine clearance	X	X ¹¹						X ¹¹						
Electrocardiography	X	X ¹¹						X ¹¹					X	
Echocardiography/multiple gated acquisition scanning	X													

Cycle	Visit	Screening Up to 21 days before day 1 of cycle 1	Cycle 1					From cycle 2 onwards					End of treatment* Within 7 (+7) days after the last dose of nanrilkefusp alfa and/or cetuximab (whichever occurs later)	Follow -up
			Day 1	Day 2 (±1 day)	Day 8 (±1 day)	Day 9 (±1 day)	Day 15 (±1 day)	Day 1 (±1 day)	Day 2 (±1 day)	Day 8 (±1 day)	Day 9 (±1 day)	Day 15 (±1 day)		
Eastern Cooperative Oncology Group performance score	X ⁴	X ¹¹						X ¹¹					X	X ⁸
Tumor assessment (CT/MRI)	X ¹⁴		Every 6 weeks (±2 weeks) starting from day 1 of cycle 1 until confirmed disease progression per iRECIST, start of next-line anti-cancer treatment, pregnancy of the patient, withdrawal of consent by the patient, or end of the study											
Nanrilkefusp alfa administration ¹⁵		X	X	X	X			X	X	X	X			
Cetuximab administration ¹⁶		X		X		X		X		X		X		
Adverse events	X		X											X ^{8,17}
Concomitant medication/ non-drug therapies	X		X											X ^{8,17}
HIV, hepatitis B and C	X													
Serum for nanrilkefusp alfa pharmacokinetics			See Table 1.1											
Serum for nanrilkefusp alfa anti-drug antibodies		X ¹¹						X ^{11,18}						X ⁸
Serum for cetuximab pharmacokinetics			See Table 1.1											
Serum for cetuximab anti-drug antibodies		X ¹¹						X ^{11,18}						X ⁸

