10.3 Appendix 3: Hy's law

Drugs are likely to cause a high rate (10-50%) of fatal liver injury or need for transplant in patients with acute hepatocellular injury sufficient to cause jaundice. Hy's law is a rule of thumb that a patient is at high risk of a fatal drug-induced liver injury if given a medication that causes hepatocellular injury (not cholestatic injury) with jaundice.

Hy's law cases have three components:

- The drug causes hepatocellular injury, generally defined as an elevated ALT or AST by 3-fold or greater above the ULN. Often with aminotransferases much greater (5-10 \times ULN).
- Among patients showing such aminotransferase elevations, they also have elevation of their serum total bilirubin of greater than 2 \times ULN, without findings of cholestasis (defined as serum alkaline phosphatase (ALP) activity less than 2 \times ULN).

No other reason can be found to explain the combination of increased aminotransferase and serum total bilirubin, such as viral hepatitis, alcohol abuse, ischemia, preexisting liver disease, or another drug capable of causing the observed injury.²⁹

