4.1.3. Treatment Period

Data collected at Day 1 will be assigned to the Treatment Period unless the time (HH:MM) of data collection and time (HH:MM) of first dose of treatment are both recorded and the data collection time is before the time of first dose of treatment. In this case, the assessment will be assigned to the screening period. If the time (HH:MM) of data collection is not recorded but the protocol and/or eCRF includes an instruction to the effect that all Day 1 assessments are to be performed prior to the first dose of treatment, the data collected at Day 1 will be assigned to the screening period. However, adverse events and medications starting on Day 1, will be assigned to the Treatment Period.

The treatment period is defined from the day of the start of study treatment to the day prior to the end of treatment visit, the end of study date, or start of new anti-cancer therapy, whichever is earliest. Date of last contact collected on the ‘Survival Status’ eCRF where status is ‘dead’ can be after end of study if the contact was with family of subject, but the latest end of study date for a ‘dead’ patient is the death date of the patient.

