4.1.4. Visit Windows

All data will be analyzed using nominal study visit as defined in the Study Schedule and eCRF. No visit windows will be applied for summary and analysis except for tumor assessment. Repeated and unscheduled measurements will be included in the listings but not be used for statistical analyses and summaries, except for the derivation of minimum/maximum values post-baseline. All tumor assessments will be considered for the time-to-event analysis.

Unscheduled visits will be identified with a numbering system that reflects the cycle they occur in by comparing the visit date against the scheduled visits and numbering in order of unscheduled visit e.g. Unscheduled Cycle 1 Day 1.01, Unscheduled Cycle 1 Day 8.01 etc. Unscheduled visits occurring on the same day as other visits will not be used in the analysis by timepoint.

Visit window for the Tumor Assessment

Additionally, for the purposes of summarizing target lesions by scheduled week, labels for assessments falling into the scheduled week of study will be derived e.g. ‘Week 6 assessment (Weeks 4 to 8)’, ‘Week 12 assessment (Weeks 10 to 14)’ etc., by assigning the assessments within the protocol specified window of every 6 weeks \pm 2 weeks (e.g. for Week 6 : C1D1 date + 28 \leq Tumor assessment date \leq C1D1 date + 56). Labels for assessments falling outside of the assessment windows would be labelled ‘Not Assigned’. In the case of multiple tumor assessments in a time window, evaluable assessments closest to the planned assessment time (or the closest non-evaluable assessment if all non-evaluable) will be considered the scheduled assessment. In the case of two assessments within a window being exactly the same distance from the centre of the window, the earliest assessment will be assigned as the scheduled assessment. Contributing assessments (e.g. target lesion assessment) should be labelled consistently with the overall tumor assessment.

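### Hy's law is summarised only by scheduled on-treatment visit, so the table can undercount patients who meet the criteria and gives no patient-level incidence

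*SAP*

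**What the plan says.** SAP 5.6.5 defines the laboratory criteria as AST and/or ALT at least 3 x ULN, concurrent total bilirubin at least 2 x ULN, and alkaline phosphatase below 2 x ULN. The number and percentage of patients meeting them "at each scheduled visit during the on-treatment period will be summarized for ASaT population". The section also plans an eDISH figure for the ASaT population and a listing of at-risk patients for the screened population. No visit limit is stated for either.

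SAP 4.1.4 sets the general rule: "Repeated and unscheduled measurements will be included in the listings but not be used for statistical analyses and summaries". It then makes a single exception, which is worded "except for the derivation of minimum/maximum values post-baseline". SAP 4.1.3 opens the Treatment Period on the first dosing day and has it run "to the day prior to the end of treatment visit, the end of study date, or start of new anti-cancer therapy, whichever is earliest".

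The biochemistry panel in protocol 8.2.5.3 includes "ALT, AST, bilirubin (direct, total), alkaline phosphatase, lactate dehydrogenase". The protocol's Schedule of activities (1.3) marks this panel at the end-of-treatment visit, which is timed "Within 7 (+7) days after the last dose of nanrilkefusp alfa and/or cetuximab (whichever occurs later"). A footnote to the same schedule allows extra samples when clinically indicated. No biochemistry is marked at the follow-up visit 30 days after the last dose.

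Protocol 10.3 describes the bilirubin component as "elevation of their serum total bilirubin of greater than 2" x ULN.

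**The concern.** Hepatic toxicity is a managed risk in this trial; protocol Table 6.2 is devoted to it. A reader of the safety report will want to know how many treated patients met the Hy's law laboratory criteria at any time after first dose. The planned table does not answer that question. It answers a narrower one, visit by visit, on a subset of the samples collected.

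Two things follow. A patient whose qualifying values lie only on an excluded sample is missing from the table, which could show no cases when there was one. Even among patients the table does capture, the rows do not give the number of distinct patients.

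**Working it through.** The plan gives no figure on this point, so there is nothing to reproduce. The check sets the rules against each type of liver sample.

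**1. Which samples reach the by-visit count**

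| Sample | Collected? | In the SAP 5.6.5 count? | Rule |
|---|---|---|---|
| Scheduled biochemistry on treatment (cycle 1 days 1, 2, 8, 9, 15; later cycles days 1, 8, 15) | Yes, protocol 1.3 | Yes, once after first dose | SAP 5.6.5 |
| Unscheduled or repeat test on treatment | Allowed, protocol 1.3 footnote | No | SAP 4.1.4 |
| End-of-treatment biochemistry | Yes, protocol 1.3 | No, if on-treatment period = Treatment Period | SAP 4.1.3 |
| Later test, including around the 30-day follow-up | Only if clinically indicated; none scheduled | No | SAP 4.1.4 |

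The exception in SAP 4.1.4 is for post-baseline minimum and maximum values. A by-visit count uses the value at the visit, not an extreme, so the exception does not bring unscheduled values into it.

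**2. Whether the end-of-treatment sample is excluded**

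SAP 5.6.5 says on-treatment period; SAP 4.1.3 defines the Treatment Period. The SAP never equates the two. If they are the same, the period closes the day before the end-of-treatment visit, or earlier if new anti-cancer therapy starts first, and the end-of-treatment sample is out. If they differ, the documents do not say where the on-treatment period ends.

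**3. Whether by-visit rows can give a patient-level count**

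Take two hypothetical cases. In case A, one patient meets the criteria at cycle 2 day 1 and again at cycle 2 day 8. In case B, two different patients meet them, one at each visit. Both tables read 1 and 1. The row sum is 1 + 1 = 2 in each, but the number of distinct patients is 1 in A and 2 in B. The largest row (1) is only a lower bound. The rows alone cannot separate A from B.

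**4. Whether the protocol shows a route to an excluded sample**

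Total bilirubin above 2 x ULN falls in the grade 2 row (above 1.5 to 3 x ULN) or the grade 3-and-above row of Table 6.2. For events related to nanrilkefusp alfa, both rows call for withholding until values return to grade 1 or below, so rechecking is implied. Under protocol 7.1, cetuximab stops if nanrilkefusp alfa has to be stopped, and the end-of-treatment visit follows. So excluded samples may be drawn in patients with a liver signal. This shows that an omission is possible; it says nothing about how often.

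**5. Pairing**

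SAP 5.6.5 requires the transaminase and bilirubin rises to be concurrent but states no window. Applied visit by visit, a patient with ALT at or above 3 x ULN at one visit and bilirubin at or above 2 x ULN only at the next appears in no row.

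**6. Cut-off**

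The SAP uses bilirubin at least 2 x ULN and protocol 10.3 uses greater than 2 x ULN. They differ only at exactly 2 x ULN. Inclusion criterion 13 admits patients with liver metastasis with ALT/AST up to 5 x ULN and bilirubin up to and including 2 x ULN. With alkaline phosphatase below 2 x ULN, a patient at that bilirubin limit and with ALT or AST of at least 3 x ULN would meet the SAP's laboratory criteria at entry but not the protocol's.

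**The case against.** The strongest reply is that no case need be lost from the report. The eDISH figure and at-risk listing have no stated visit limit, all laboratory values are listed with high/low flags (SAP 5.6.4), and the minimum/maximum exception could bring unscheduled peaks into eDISH. Clinically relevant laboratory abnormalities are also recorded as adverse events (protocol 8.3.8.1) and collected to 90 days after the last dose, and the TEAE tables are not tied to scheduled visits. In a small single-arm trial an attentive reader could find each patient. This stands, and it limits the consequence: what is wrong is the count. It does not remove the point, because none of these outputs gives the number of patients meeting the laboratory criteria, and the SAP does not say which values feed eDISH. Table and figure could disagree.

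Several stronger readings are tempting, and the documents do not support them:

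- **That Hy's law cases mostly appear on unscheduled or end-of-treatment tests.** Neither document says so. Scheduled biochemistry is frequent, and many cases could be caught there.
- **That a dose-limiting toxicity could be hidden.** Hy's law cases are DLTs in the safety cohorts, but SAP 5.6.2 identifies DLTs from the adverse event page, not from this table.
- **That the cut-off mismatch adds to the undercount.** The SAP threshold is the wider one, so it catches every case the protocol's threshold catches.
- **That one missed case is 1/52 = 1.9%.** The 52 is the efficacy-population target; the ASaT size is not stated. The ratio would describe one hypothetical case and is not evidence that a miss is likely.

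**Conclusion.** The point holds as a reporting gap. As written, the Hy's law table leaves out unscheduled and repeat tests. It leaves out the end-of-treatment sample too if the on-treatment period is the Treatment Period of SAP 4.1.3; that second exclusion is an inference, and the undefined term is itself a defect. The table can undercount, and it yields no patient-level incidence.

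The undercount equals the number of patients whose qualifying values lie only on excluded samples. It may be zero, and the documents give no basis for a figure.

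One caveat: SAP 5.6.5 announces a set of categories for the liver summary, but no list follows in the text available to me, possibly because of PDF conversion. If that list contains an any-time patient-level count, the point reduces to the definition, pairing, eDISH and cut-off items.

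**What to change.** In SAP 5.6.5:

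1. Add a patient-level count, each patient once, of the Hy's law laboratory criteria met on any sample after first dose. Include unscheduled and end-of-treatment samples and any later clinically indicated sample. State that this count is an exception to the summary rule in SAP 4.1.4. Do not describe it as covering scheduled tests at the 30-day follow-up, because there are none.
2. Define the on-treatment period and say whether it includes the end-of-treatment visit.
3. State the window within which ALT/AST and bilirubin values are paired.
4. Use the same values for the eDISH figure, so that figure and count agree.
5. Reconcile the bilirubin cut-off between SAP 5.6.5 and protocol 10.3.
6. Keep the by-visit table as supplementary.

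The cost is SAP wording and some programming. The samples are already scheduled or allowed by the protocol and listed under the SAP, so no new data collection is needed. SAP 5.6.6 already plans patient-level maximum changes for vital signs, so this kind of output is not new to the plan.
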